4.13.1 Primary Safety Analysis

The primary safety endpoint is the development of inhibitors against FIX.

4.13.2 Inhibitors to Factor IX

The development of inhibitors against FIX is defined as any inhibitor identified at a concentration of ≥ 0.6 BU/mL and confirmed with retesting to be ≥ 0.6 BU/mL. Both tests must be performed by a central laboratory. The incidence of inhibitor development and 95% CI will be presented separately for PTPs and PUPs in the safety population.

For estimating the incidence of inhibitors against FIX in PTPs, the numerator will include all PTPs with inhibitors regardless of EDs to rIX-FP; the denominator will include PTPs with at least 100 EDs plus PTPs with less than 100 EDs who have confirmed inhibitors as follows:

Incidence of inhibitors against FIX in PTPs = number of PTPs who develop inhibitors up to 100 EDs (i.e. ≤ 100 EDs) / (total number of PTPs with at least 100 EDs (≥ 100 EDs) + PTPs with < 100 EDs who have confirmed inhibitors)

PTPs not tested at ≤ 100 EDs will be excluded.

For estimating the incidence inhibitors against FIX in PUPs, the numerator will include all PUPs with inhibitors to rIX-FP; the denominator will include PUPs with at least 50 EDs plus PUPs with less than 50 EDs but with confirmed inhibitors as follows:

Incidence of inhibitors against FIX in PUPs = number of PUPs who develop inhibitors / (PUPs with ≥ 50 EDs + PUPs with < 50 EDs who have confirmed inhibitors).

PUPs not tested at ≤ 50 EDs will be excluded.

The number of subjects with antibodies to plasma-derived factor IX (pdFIX), recombinant FIX (rFIX), albumin, and CHO cells will be tabulated by age group and total.

The two-sided Wald and Clopper-Pearson 95% CI ([Clopper C](#), [Pearson ES](#)) for the incidence of FIX inhibitor formation will be provided. Example SAS code for this procedure is provided below:

```
proc freq data=data order=freq;
  tables inhibitor / binomial(exact);
  weight pos;
run;
```

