Subjects will be treated in the study center or medical facility under medical supervision during the initial 10 to 20 treatment with rIX-FP. The first 2 infusions must be monitored on-site for at least 3 hours.

- A: PK can start at Day 1 as the first dose or/and during the study after ≥ 7 days washout from the previous rIX-FP dose, when the subject is in non-bleeding state. See [Table D](#) for PK sampling time points. (Day 1 is the day subject receives his first dose with rIX-FP)
- B: Tests that require blood sample for screening period (from ICF day to Day 1 prior to dose) can be divided to multiple days or combined with Day 1 tests. The screening day can be the same day for first dose of rIX-FP (either on-demand, prophylaxis or PK dose).
- C: Vital signs include blood pressure, temperature and heart rate.
- D: Includes liver and renal function test (Albumin, Alanine Aminotransferase, Aspartate Aminotransferase, Alkaline Phosphatase, Bilirubin, Direct Bilirubin, Protein, Blood Urea Nitrogen or Urea, and Creatinine).
- E: Documented biochemistry & hematology results from 6 months prior to screening are acceptable; otherwise, samples may be collected during the screening period or at Day 1. Samples for antibodies/inhibitor must be collected during the screening period or prior to first dose of rIX-FP.
- F: A sample that tests positive for antibodies against rIX-FP will be retested to discriminate between pdFIX, rFIX and albumin antibodies.
- G: Retain samples will be collected prior to the first dose of rIX-FP for potential serology testing at a later date.
- H: Optional samples at Day 3 or Day 7 of PK assessment, or during the month 1, 2 or 3 for FIX activity if feasible.
- I: If subjects receive treatment for less than 3 doses per month, they may omit the site visit(s) until they received ~ 5 doses.
- J: FIX activity tested at local Laboratory if no previous FIX data available in medical records.
- K: Subject eDiary may be dispensed once caregiver is trained to administer rIX-FP at home, but not prior to receiving a minimum of 10 infusions at the study center or medical facility under medical supervision.
- L: End of Study for Arm 4 is the Month 36 visit.

Table of Contents

| | |
|--|----|
| SIGNATURE ON BEHALF OF SPONSOR | 3 |
| SIGNATURE OF INVESTIGATOR | 4 |
| REVISION HISTORY | 5 |
| PROTOCOL SYNOPSIS..... | 8 |
| TABLE A - SCHEDULE OF ASSESSMENTS: TREATMENT PERIOD (ARMS 1, 2 AND 3) | 21 |

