2.1.2 Primary Endpoints

- The total number of subjects who develop inhibitors against FIX during the approximately 3-year participation in this study.
- PK parameter of incremental recovery (IU/dL per IU/kg) of 50 IU/kg rIX-FP (Arm 4 only).

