11.3.3.1 Primary Safety Analysis

The number and proportion of subjects with positive tests for inhibitors to FIX during the study will be tabulated. Subjects must have two tests that are positive to be classified as having an

inhibitor. Inhibitor antibodies against FIX will be categorized as low titer (≥ 0.6 to 5 BU/mL) and high titer (> 5 BU/mL). A two-sided 95% exact Clopper-Pearson binomial confidence interval (one-sided if no events are observed) for inhibitor development among subjects treated with rIX-FP, by PTP and PUP, will be presented.

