This document presents the statistical analysis plan (SAP) for CSL Behring GmbH, Protocol No. CSL654_3003: A Phase 3b Open-label, Multicenter, Safety and Efficacy Extension Study of a Recombinant Coagulation Factor IX Albumin Fusion Protein (rIX-FP) in Subjects with Hemophilia B.

This analysis plan is based on the protocol amendment 6 dated 03 February 2020, final electronic case report form (eCRF) dated 17 May 2017, and the SAP version 3 dated 20 April 2018. This SAP contains all analyses for the previously treated patients (PTPs), and the updated contents for the previously untreated patients (PUPs).

In the event that the statistical methods specified in this SAP differ from those specified in the protocol, the statistical methods specified in the SAP will supersede the statistical methods described in the protocol.

2 Study Objectives

- Main Study
 - Primary Objective
 - The primary objective of this study is to evaluate the safety of rIX-FP as measured by new cases of inhibitors against FIX in subjects, including PUPs, with severe hemophilia B. The PK parameters in PUPs will also be collected.
 - Primary Endpoint(s)
 - The total number of subjects who develop inhibitors against FIX during the approximately 5-year participation in this study.
 - PK parameter of incremental recovery (IU/dL per IU/kg) of 50 IU/kg rIX-FP (Arm 4 only)
 - Secondary Objective(s)

[figure not shown]
The secondary objectives of the study are:

 - To evaluate the efficacy of rIX-FP routine prophylaxis when administered at various treatment intervals.
 - To compare the efficacy of rIX-FP routine prophylaxis between 2 different treatment intervals and versus on-demand treatment.
 - To further evaluate the safety of rIX-FP.
 - To evaluate the efficacy of treatment for bleeding episodes in PUPs.
 - Secondary Endpoint(s)
 - Annualized bleeding rate (ABR) for spontaneous treated and total treated bleeds for each assigned treatment interval (7 days, 10 days, 14 days, and 21 days).
 - Comparison of the annualized spontaneous bleeding rate (AsBR) and ABR between:

- 14-day routine prophylactic treatment in this study compared with on-demand only treatment from Study CSL654_3001 Arm 2.
- 7-day prophylaxis regimen with the 14-day prophylaxis regimen.
- 7-day prophylaxis regimen with the extended prophylaxis regimen (10-day or 14-day).
- Total number of exposure days of rIX-FP
- Consumption of rIX-FP during routine prophylaxis expressed as IU/kg per month per subject.

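### SAP 4.13.2: a PUP can count as inhibitor-free without a negative test at or after ED 50, and the PTP sentence and formula use different numerators (minor)

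*SAP*

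**What the plan says.** **Endpoint.** Protocol 2.1.2 defines it as "The total number of subjects who develop inhibitors against FIX during the approximately 3-year participation in this study". SAP Section 2 has "The total number of subjects who develop inhibitors against FIX during the approximately 5-year participation in this study". The nominal durations differ, but neither version limits cases by exposure.

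**Protocol analysis.** Protocol 11.3.3.1 calls for an exact interval "for inhibitor development among subjects treated with rIX-FP, by PTP and PUP, will be presented". That is a proportion of all treated subjects.

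**SAP analysis.** SAP 4.13.2 uses exposure-restricted denominators: PTPs with at least 100 EDs, or PUPs with at least 50, plus anyone below the threshold who has a confirmed inhibitor.

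- PTP numerator in the sentence: "the numerator will include all PTPs with inhibitors regardless of EDs to rIX-FP".
- PTP numerator in the formula which that sentence introduces: "number of PTPs who develop inhibitors up to 100 EDs".
- PUP numerator: sentence and formula agree, with no ED limit.
- Testing conditions: "PTPs not tested at ≤ 100 EDs will be excluded" and "PUPs not tested at ≤ 50 EDs will be excluded".

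**Sampling in PUPs.** Protocol Table D, note E: "Samples for antibodies/inhibitor must be collected during the screening period or prior to first dose of rIX-FP". Later inhibitor samples are set out in Protocol 8.9.4.2, 8.9.4.3, 8.9.5 and 8.9.7.

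**The concern.** A denominator restricted to subjects with enough exposure is meant to ensure that each non-case had a fair chance to show an inhibitor and was looked at after that exposure. The SAP secures the exposure but not the later look. Its testing condition faces backwards: it asks for a test at or before the threshold and none at or after it. A PUP whose last valid test was early, and who then reached 50 EDs, enters the denominator as inhibitor-free.

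For PTPs, two programmers working from the same paragraph could produce different numerators. A PTP whose confirmed inhibitor first appears after 100 EDs is in the denominator both ways, but is a case under the sentence and a non-case under the formula. The endpoint itself has no such cap.

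At stake are the proportion and interval that report the primary safety endpoint. The PUP half is the live one, because SAP 3.4 says this version concentrates on Arm 4.

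**Working it through.** The documents give no incidence or power figure for this estimate (SAP 3.3 says the sample size is not power-based), so there is nothing of the plan's own to reproduce. The check compares wording and then shows what one subject changes.

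**1. Does the PUP testing condition exclude anyone?** A sample taken before the first dose is at 0 EDs, which is at or below 50. It is mandatory, so every compliant PUP passes. The condition says nothing about later tests.

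**2. How often could a PUP lack a later test?** Arm 4 inhibitor samples are due at Months 1 to 6, 9, 12, 18, 24 and 30, at 50 EDs, and at end of study (Month 36 by Table D, note L).

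- Weekly dosing from Day 1: ED 50 falls on Day 1 + 49 × 7 = Day 344, which is month 11.3 (30.4-day months) or 12.3 (28-day months). Tests at or after it: 6 or 5.
- Weekly dosing from Month 12 with 0 to 20 earlier EDs: ED 50 falls between months 18.7 and 24.2. Tests at or after it: 3 to 4.
- Participation ending at 50 EDs, which Protocol 3.3 gives as an alternative duration: the 50-ED and end-of-study samples, or one if the visits are combined as Protocol 8.9.7 allows. Tests: 1 to 2.

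Every scheduled path therefore gives at least one test at or after ED 50. An untested non-case needs a missed or invalid sample.

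**3. Effect in PUPs.** Inputs: the minimum of 13 PUPs (SAP 3.3), the two-sided 95% Clopper-Pearson interval (SAP 4.13.2), and one PUP without the later test (assumed). The upper limit is 1 − 0.025^(1/n) for zero cases, and the 97.5% quantile of Beta(2, n − 1) for one case.

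| Cases | Tested PUPs only | Untested PUP counted as a non-case |
|---|---|---|
| 0 | 0/12 = 0%, upper 26.5% | 0/13 = 0%, upper 24.7% |
| 1 | 1/12 = 8.3%, upper 38.5% | 1/13 = 7.7%, upper 36.0% |

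Under the protocol's one-sided limit for zero cases, 1 − 0.05^(1/n), the figures are 22.1% (n = 12) and 20.6% (n = 13).

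**4. Effect in PTPs.** Assume one PTP whose confirmed inhibitor first appears after 100 EDs. This is possible, since SAP 4.7 tabulates PTP exposure up to 300 EDs and more. Evaluable PTPs are taken as 83 (the planned 96 less 13 PUPs, and the final PTP number in the revision history) or 50 (the target in SAP 3.3).

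| Evaluable PTPs | Formula | Sentence |
|---|---|---|
| 83 | 0/83 = 0%, upper 4.35% | 1/83 = 1.2%, upper 6.53% |
| 50 | 0/50 = 0%, upper 7.11% | 1/50 = 2.0%, upper 10.65% |

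**5. Which EDs count for PTPs?** SAP 4.13.2 does not say. SAP 3.2 and 3.3 tie the 100-ED target to all of the sponsor's rIX-FP studies. Protocol 11.3 makes this study alone the default unless otherwise indicated. SAP 4.7 reports both. An inhibitor count from this study over a cumulative-exposure denominator would mix two periods.

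**The case against.** The strongest reply is that little turns on this.

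- **PTPs.** SAP 3.1 says they were already analysed in the report of 14 March 2019 and will not be analysed again here. The phrase about counting regardless of EDs may mean only that cases below 100 EDs are kept, which leaves the cap standing without contradiction. A late confirmed case would still appear in the uncapped tabulation of Protocol 11.3.3.7, and an adverse event associated with a confirmed inhibitor is reported as serious (Protocol 9.1.2).
- **PUPs.** The sentence and formula agree, the schedule supplies later tests, and Protocol 4.2.2 asks for end-of-study assessments on withdrawal. The analysis is descriptive (SAP 4.1), with no decision threshold attached.
- **Denominator.** The SAP may override the protocol, as its introduction states. Compared with all treated subjects, dropping low-exposure non-cases while keeping low-exposure cases can only leave the proportion unchanged or raise it.

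Most of this stands and limits the severity. It does not remove the gap. Missed samples are foreseeable: SAP 4.5 plans a summary of PUP visits missed because of COVID-19, Protocol 8.9.4.2 asks for a prompt make-up inhibitor visit only during the first 20 EDs, and Protocol 4.2.2 promises only attempts after withdrawal. Nor does the text settle which PTP reading is meant.

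A reader might infer that the plan will routinely count untested PUPs as inhibitor-free, or that the reported PTP rate is too low. The documents support neither. Every scheduled PUP path has a test at or after ED 50, and nothing here shows which PTP numerator was used or that any case arose after 100 EDs.

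**Conclusion.** The point holds as a minor fault in the primary safety analysis.

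For PUPs, evaluability as a non-case does not depend on a negative test at or after ED 50. With 13 PUPs and one lacking that test, a zero-case result keeps its 0% estimate and only the upper limit falls, by about 1.8 percentage points (26.46% to 24.71%). With one case, the estimate falls by about 0.6 points (8.33% to 7.69%). It would be wrong to say that the proportion always falls.

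For PTPs, the sentence and formula differ on cases after 100 EDs. This has an effect only if the March 2019 report followed the formula and such a case occurred; neither can be established from the documents.

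The sizes rest on assumed counts: one PUP without the later test, one late PTP case, and 50 to 83 evaluable PTPs. The test counts rest on the assumed month length and 0 to 20 earlier EDs. The wording faults rest on none of these. That SAP Section 8 does not list the exposure-restricted denominator is housekeeping.

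**What to change.** In SAP 4.13.2:

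1. Use one numerator in each group: every confirmed inhibitor. Always keep a case, whatever its exposure or the timing of its tests.
2. Replace both testing lines with one rule. A non-case is evaluable only with at least 50 EDs (PUP) or 100 EDs (PTP) and a valid negative inhibitor test at or after that ED.
3. Show beside it the proportion among all treated subjects, as Protocol 11.3.3.1 specifies.
4. For PTPs, state the period, and count inhibitors and EDs over the same one: both in this study, or both cumulative across rIX-FP studies.
5. When the PTP report is integrated into the final report (Protocol 14.7), check which numerator its table used. Correct it only if the formula was used and a case arose after 100 EDs. If a rate by 100 EDs is kept, label it so and list later cases beside it.
6. List the exposure-restricted denominator in SAP Section 8.

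The cost is SAP wording, one evaluability flag built from samples already scheduled, one extra proportion, and one check of a finished report. No visit or sample is added. The downside is a slightly smaller evaluable PUP denominator and a wider interval if a subject lacks the later test; the all-treated proportion keeps that subject in view.

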Consumption of rIX-FP will be summarized with descriptive statistics according to treatment interval and overall.

For subjects from Study CSL654_3002, responses to the treatment satisfaction questionnaire and age group-specific CCI questionnaire (Hemo-Sat and CCI, respectively) will be summarized with descriptive statistics.

Data from the surgery substudy will be summarized as case narratives or with descriptive statistics or counts, where appropriate.

Safety Analyses

The number and proportion of subjects with positive tests for inhibitors to FIX during the study will be tabulated separately for PTPs (Arm 1, 2 and 3) and PUPs (Arm 4). Inhibitor antibodies against FIX will be categorized as low titer (≥ 0.6 to 5 BU/mL) and high titer (> 5 BU/mL). An exact 95% binomial confidence interval for inhibitor development among subjects treated with rIX-FP will be presented.

The number and proportion of subjects with adverse events and serious adverse events, which are study-emergent, will be tabulated. Laboratory, vital signs and physical examination assessments will be summarized.

Pharmacokinetic Analyses

Incremental recovery and FIX activity levels will be summarized using descriptive statistics.

See Appendix 2 for the statistical analyses planned in the SC substudy.

Further details regarding the statistical analysis will be provided in the Statistical Analysis Plan (SAP).

Interim Analyses

No interim analyses are planned. The following analyses are planned before study closure:

1. The final analysis of the SC substudy data will be conducted once all subjects have completed the SC substudy.

-
2. The final analysis of PTPs (including surgical data from PTPs) will be conducted when all PTPs have completed the study.

In addition, safety, efficacy and / or PK data and subject characteristics may be reported to regulatory authorities before study closure.

TABLE A - SCHEDULE OF ASSESSMENTS: TREATMENT PERIOD (ARMS 1, 2 AND 3)

| Assessments | Day 1 ^B Arm 1 & 2 | Month ^A | | | | | | 50 EDs ^D | End of Study |
|---|---------------------------------|---------------------------------|----------------|----------------|----|----------------|----------------|---------------------|----------------|
| | | 3 ^C | 6 ^L | 9 ^C | 12 | 18, 30, 42, 54 | 24, 36, 48, 60 | | |
| Informed consent | X | | | | | | | | |
| Demographics, lead-in study data | X | | | | | | | | |
| Eligibility assessment | X | | | | | | | | |

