6.7.7.2 Additional Safety Assessments

Inhibitors and Antibodies

The number and percentage of subjects with inhibitors against FIX ([Section 4.13.2](#)) and 95% exact [Clopper-Pearson](#) CI will be presented as applicable for all subjects in the surgical population. The number and percentage of subjects with positive or negative results to the following antibodies also will be included:

- rIX-FP
- pdFIX
- rFIX
- albumin
- antibodies against CHO cells

Change in Hemoglobin

The absolute value and change in hemoglobin from the last pre-operative measurement to the intraoperative and post-operative measurements (0, 24, 48, 72 hours, and end of surgical substudy) will be summarized with descriptive statistics. Descriptive statistics for the lowest intraoperative and post-operative values also will be included.

Change in Vital Signs

The absolute value and change in vital signs (i.e. SBP, DBP, heart rate, and temperature) from the last pre-operative measurement to the intraoperative and post-operative

measurements (0, 24, 48, 72 hours, and end of surgery substudy) will be summarized with descriptive statistics. Descriptive statistics for the lowest intraoperative and post-operative values also will be included.

Comparison of Predicted and Intraoperative Estimated Blood Loss during Surgery

Descriptive statistics will be provided for the average and maximum predicted blood loss (mL) and estimated actual blood loss during the surgery substudy.

Comparison of Predicted and Actual Transfusion Requirements during Surgery

Descriptive statistics will be provided for the predicted and actual units of packed red blood cells, whole blood, and any other transfusion products utilized during surgery.

7 Subcutaneous Substudy

[figure not shown]

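### The SAP adds a Wald interval to the exact interval for the primary inhibitor incidence without saying which to interpret; with at least 13 PUPs planned, the Wald interval is not valid

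*SAP*

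**What the plan says.** Protocol 11.3.3.1 gives one interval for inhibitor development, by PTP and PUP: "A two-sided 95% exact Clopper-Pearson binomial confidence interval (one-sided if no events are observed"). The Safety Analyses part of the synopsis agrees: "An exact 95% binomial confidence interval for inhibitor development among subjects treated with rIX-FP will be presented".

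SAP 4.13.2 says that the incidence and its 95% CI "will be presented separately for PTPs and PUPs in the safety population", and then specifies "The two-sided Wald and Clopper-Pearson 95% CI". Neither interval is named as the one to interpret. For PUPs, "the denominator will include PUPs with at least 50 EDs plus PUPs with less than 50 EDs but with confirmed inhibitors", so the denominator can be smaller than the number enrolled. The example code in the same section requests "tables inhibitor / binomial(exact"), and the only literature reference attached to the interval is the one for Clopper-Pearson.

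Three other places in the SAP bear on this:

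- The introduction states that where the two documents differ, "the statistical methods specified in the SAP will supersede the statistical methods described in the protocol".
- Section 6.7.7.2 uses the exact Clopper-Pearson interval alone for inhibitors in the surgery substudy: the 95% exact "CI will be presented as applicable for all subjects in the surgical population".
- Section 8 lists deviations from the protocol's analyses. Neither its PTP entries nor its PUP entry, which concerns bleeding rates only, mentions a Wald interval.

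**The concern.** The precedence clause lets the SAP depart from the protocol, but it cannot choose between two intervals named in one SAP sentence. The code and the reference point to the exact interval, yet the sentence requires both, and no reason is given for adding the second.

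The Wald interval relies on a normal approximation that breaks down with a small denominator and few events. SAP 3.1 says the PTPs were analysed in a report dated 14 March 2019, so the PUP incidence is the result still to come. In a descriptive analysis the interval is the only statement of uncertainty. For a safety endpoint the error also runs in the unhelpful direction: with few events the Wald upper limit is too low.

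**Working it through.** The documents state no precision, coverage or interval width for inhibitor incidence, so there is no figure of the plan's own to reproduce.

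**Inputs.** At least 13 PUPs (SAP 3.3; Protocol 11.1). 95% two-sided (SAP 4.1 and 4.13.2). The documents give no event count, evaluable denominator or true incidence. I therefore assume denominators of 10, 13 and 16, event counts of 0, 1 and 2, and true incidences of 2%, 5% and 10%.

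**Formulas.** With x events in n subjects and p = x/n:

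- Wald: p ± 1.96 × √(p(1 − p)/n).
- Clopper-Pearson: lower limit = 2.5% quantile of Beta(x, n − x + 1), upper limit = 97.5% quantile of Beta(x + 1, n − x). At x = 0 the upper limit is 1 − 0.025^(1/n).

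**Zero events, n = 13.** Wald: 0 ± 1.96 × √0 = 0 to 0%. Exact upper limit: 1 − 0.025^(1/13) = 24.7%.

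**One event, n = 13.** p = 1/13 = 0.0769; √(0.0769 × 0.9231/13) = 0.0739; 1.96 × 0.0739 = 0.1449. Wald: -6.8% to 22.2%. Exact: 0.2% to 36.0%. Gap in the upper limits: 36.03 − 22.18 = 13.85 points.

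**Both intervals (%) over the assumed denominators.**

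| Events | Method | n = 10 | n = 13 | n = 16 |
|---|---|---|---|---|
| 0 | Wald | 0 to 0 | 0 to 0 | 0 to 0 |
| 0 | Exact | 0 to 30.8 | 0 to 24.7 | 0 to 20.6 |
| 1 | Wald | -8.6 to 28.6 | -6.8 to 22.2 | -5.6 to 18.1 |
| 1 | Exact | 0.3 to 44.5 | 0.2 to 36.0 | 0.2 to 30.2 |
| 2 | Wald | -4.8 to 44.8 | -4.2 to 35.0 | -3.7 to 28.7 |
| 2 | Exact | 2.5 to 55.6 | 1.9 to 45.4 | 1.6 to 38.3 |

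**Actual coverage.** For each assumed true rate, add the binomial probabilities of the event counts whose interval contains that rate. Example at n = 13 and a true 5%:

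- P(0) = 0.95^13 = 51.3%, P(1) = 35.1%, P(2) = 11.1%, P(3) = 2.1%.
- The Wald interval contains 5% only at 1, 2 or 3 events: 35.12 + 11.09 + 2.14 = 48.4%.
- The exact interval contains it at 0, 1 or 2 events: 51.33 + 35.12 + 11.09 = 97.5%.

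| True incidence | Wald, n = 10 / 13 / 16 | Exact, n = 10 / 13 / 16 |
|---|---|---|
| 2% | 18.3 / 23.1 / 27.6% | 98.4 / 99.8 / 99.6% |
| 5% | 40.0 / 48.4 / 55.9% | 98.8 / 97.5 / 99.3% |
| 10% | 65.0 / 73.9 / 81.1% | 98.7 / 99.4 / 98.3% |

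At n = 13 and a true 5%, the Wald upper limit lies below the truth with probability 51.3%, which is the chance of seeing no event.

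**Higher rates.** At n = 13 Wald coverage is 87.2% at a true 15%, 93.8% at 20% and 91.8% at 30%.

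**The case against.** The strongest reply is that nothing valid is lost. The SAP still provides Clopper-Pearson, the protocol already names it, and the reference, the code and the surgery substudy all point the same way, so a reader would probably rely on it. The endpoint itself is a count, PUP analyses are descriptive (SAP 4.1), formal safety comparisons are not planned unless specified (SAP 4.13) and the sample size is not based on power (SAP 3.3). The failures are also easy to see: a zero-width or negative interval printed next to an exact one should warn the reader. Harm requires a report to quote Wald alone, which nothing in the plan proposes.

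Most of this stands, and it limits the weight of the point. It does not justify pre-specifying the second interval on the primary safety endpoint with neither one designated.

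A second reply is that the poor coverage depends on assuming low true rates. That is correct for the coverage figures, since at n = 13 Wald comes close to nominal near 20%. It does not rescue the zero-event case, where the width is zero at any denominator, or the negative lower limits at one or two events for n from 10 to 16. Neither depends on the true rate.

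A third reply is that removing Wald for PUPs only leaves the PTP wording with the same defect: at the upper-bound denominator of 83 PTPs, zero events give 0 to 0% against an exact 0 to 4.3%. That is also true. The PTP specification is left alone only because that analysis has been reported; naming the exact interval for both groups would do no harm.

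**Conclusion.** The concern holds. The SAP adds an interval that the protocol does not contain, designates neither of the two, and does not log the addition. At the planned PUP size the added interval is falsely reassuring: zero width at no events, an upper limit about 14 points below the exact one at 1 of 13, and coverage of 23.1% to 73.9% at n = 13 for assumed true rates of 2% to 10%. The coverage figures rest on the assumed denominators and rates, and the intervals on the assumed denominators and event counts; the collapse at zero events rests on no assumption beyond seeing none.

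The consequence is minor to moderate. The correct interval is still reported and no decision rule depends on the choice, but a report could quote the wrong error bars. It should be corrected before the PUP analysis.

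A smaller matter goes with it. The protocol makes the interval one-sided when there are no events. The SAP settles this as two-sided through its precedence clause, its general convention in 4.1 and the sentence in 4.13.2. Only the Section 8 entry is missing.

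**What to change.** In SAP 4.13.2, remove the Wald interval for PUPs, for example: *For PUPs, the two-sided Clopper-Pearson 95% CI will be provided at every event count, including zero, and is the interval interpreted.* At minimum, name Clopper-Pearson as the interval to interpret and label Wald supplementary.

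In the PUP part of Section 8, record that the interval stays two-sided at zero events, replacing the protocol's one-sided rule. If Wald is kept, record that it was added.

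The cost is one phrase in 4.13.2 and one entry in Section 8. No new data are needed, the exact limits do not change, and the reported PTP analysis is untouched.

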- Secondary Endpoint(s)**
- Annualized bleeding rate (ABR) for spontaneous treated bleeds and total treated bleeds for each assigned treatment interval (7 days, 10 days, 14 days, and 21 days).
 - Comparison of the AsBR and ABR between:
 - 14-day routine prophylactic treatment in this study compared with on-demand only treatment from Study CSL654_3001 Arm 2.
 - 7-day prophylaxis regimen with the 14-day prophylaxis regimen.
 - 7-day prophylaxis regimen with the extended prophylaxis regimen (10-day or 14-day).
 - Consumption of rIX-FP during routine prophylaxis expressed as IU/kg per month per subject.
 - Incidence of adverse events and related adverse events to rIX-FP over the course of the study.
 - Hemostatic response to treatment of bleeding episodes with rIX-FP as assessed by the investigator based on a 4-point scale (Arm 4 only).

CCI

CCI

A large black rectangular redaction box covering the majority of the page content. The letters "CCI" are printed in red at the top left corner of the redacted area.

CCI

A very large black rectangular redaction box covering almost the entire page content. The letters "CCI" are printed in red at the top left corner of the redacted area.

| | |
|---------------------------|---|
| Study Design | Multicenter, open-label, phase 3b study. |
| Number of Subjects | This study will enroll approximately 96 male subjects, including all eligible subjects from rIX-FP lead-in studies, approximately 10 subjects requiring major non-emergency surgery and at least 13 PUPs. |

Any subjects requiring non-emergency surgery or any subjects in Arm 4 requiring minor surgery during the course of the study may be enrolled in the surgery substudy. Up to a maximum of 24 subjects will enroll in the SC substudy.

Study Duration

For subjects in Arms 1, 2, and 3, the duration of the study for an individual subject is expected to be approximately 5 years or the time it takes to achieve a total of 100 EDs during the subject's enrollment in any CSL-sponsored rIX-FP studies. For subjects in Arm 4, the duration of the study is expected to be approximately 3 years or the time it takes to achieve a total of 50 EDs. The study may be stopped at a specific study site after all subjects at the site have completed the 5-year study period or ≥ 50 subjects overall have achieved a total of 100 EDs or after regulatory approval and rIX-FP becomes commercially available in the respective country.

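### The example SAS code for the FIX inhibitor interval (SAP 4.13.2) estimates the more frequent level, normally subjects without an inhibitor, not the incidence that the text specifies

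*SAP*

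**What the plan says.** SAP 4.13.1 names inhibitor development as the primary safety endpoint. SAP 4.13.2 defines the event: "The development of inhibitors against FIX is defined as any inhibitor identified at a concentration of" 0.6 BU/mL or more, confirmed on retest by a central laboratory. The numerator is subjects who develop inhibitors. The denominators, separate for PTPs and PUPs, are subjects who reached 100 or 50 exposure days respectively, plus confirmed cases who did not. Two-sided 95% Wald and Clopper-Pearson intervals "for the incidence of FIX inhibitor formation will be provided".

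The section then says: "Example SAS code for this procedure is provided below". The block opens with "proc freq data=data order=freq". Its table request is "tables inhibitor / binomial(exact", with the bracket closed straight after and no LEVEL= option. It ends with `weight pos`. The SAP does not define `pos`, does not give the coding of `inhibitor`, and has no format or sort rule that would list the positive level first.

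Protocol 11.3.3.1 has the same target: "A two-sided 95% exact Clopper-Pearson binomial confidence interval (one-sided if no events are observed) for inhibitor development among subjects". SAP 6.7.7.2 sends the surgery-substudy inhibitor analysis back to 4.13.2 for its definition.

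**The concern.** The text and the code attached to it point at opposite levels of a binary variable. The text wants the proportion with an inhibitor. The code lets the data choose the level by frequency, and for an uncommon event that selects the subjects without one.

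The zero-event case needs most care. The protocol foresees it by giving it its own interval rule. Under SAP 9.1 a zero numerator is shown without a percentage, so the interval would carry the quantitative message. In that case the code as written has no inhibitor level to report at all.

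This is the only code the SAP gives for its primary safety interval. SAP 4.1 assigns the programming to a contract research organization, and the SAP's opening section says its methods override the protocol's. An example in that position should compute the quantity beside which it stands.

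**Working it through.** **Plan's own figure.** There is none to reproduce. Neither document states an expected inhibitor rate or interval width, and Protocol 11.1 says that the sample size is not based on power.

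**Inputs**
- Code options: SAP 4.13.2, as above.
- Weight variable: `pos` is read as the cell count for each level of `inhibitor`. This is an assumption.
- Illustrative n: 13, from the Number of Subjects entry in the protocol synopsis, "approximately 10 subjects requiring major non-emergency surgery and at least 13 PUPs". This is minimum enrolment. The evaluable number under SAP 4.13.2 could differ.
- PROC FREQ behaviour: ORDER=FREQ sorts levels by descending weighted count. BINOMIAL without LEVEL= estimates the first listed level. WEIGHT without ZEROS ignores rows with weight 0. This is general software knowledge, not stated in the documents, and SAS was not available to run the block.

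**Which level is reported.** With x cases among n subjects, the no-inhibitor level comes first when n − x > x. For n = 13 that means x ≤ 6, and the code then reports (13 − x)/13.

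**Clopper-Pearson limits.** For x events in n:
- lower = Beta quantile at 0.025 with parameters (x, n − x + 1), or 0 if x = 0;
- upper = Beta quantile at 0.975 with parameters (x + 1, n − x), or 1 if x = n.

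At x = 0 the upper limit is 1 − 0.025^(1/13) = 0.2471. At x = n the lower limit is 0.025^(1/13) = 0.7529.

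| Cases of 13 | Incidence intended (95% CI), % | Output of code as written (95% CI), % |
|---|---|---|
| 0 | 0 (0 to 24.71) | 100 (75.29 to 100) |
| 1 | 7.69 (0.19 to 36.03) | 92.31 (63.97 to 99.81) |
| 2 | 15.38 (1.92 to 45.45) | 84.62 (54.55 to 98.08) |
| 6 | 46.15 (19.22 to 74.87) | 53.85 (25.13 to 80.78) |
| 7 | 53.85 (25.13 to 80.78) | 53.85 (25.13 to 80.78) |

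**Mirror check.** The printed lower limit is 1 minus the intended upper limit, and the reverse. For one case, 1 − 0.3603 = 0.6397 and 1 − 0.0019 = 0.9981. Wald limits mirror in the same way.

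**When the code would be right.** Seven or more of 13 must be cases. The chance of that is about 0.000001 at an assumed true rate of 5%, 0.0001 at 10%, 0.7% at 20% and 6% at 30%.

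**Zero cases.** A summarised inhibitor row with weight 0 is ignored without ZEROS. Adding LEVEL= alone would then name a level that is not in the table.

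**The other reading of `pos`.** If it is a 0/1 flag for a positive subject, negative subjects get weight 0 and are ignored. With x ≥ 1 cases the output is x/x = 100%, which is also not the incidence.

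**The case against.** The strongest reply is that the block is introduced as an example. The dataset name is a placeholder and two variables are undefined, so nobody can run it without making decisions, and the prose that governs those decisions is right on event, numerator, denominators and interval method. No analysis choice is in error. The result would also give itself away: an inhibitor incidence of 92% or 100% beside a count of one or zero would be noticed at once, and the right interval is recovered by subtracting the printed limits from 1. SAP 4.13 plans no formal safety comparisons, so no test or decision rule depends on it.

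All of that stands and it limits the severity. It does not make the code correct, because neither reading of `pos` considered above gives the stated incidence.

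A reader might go further in two ways that the documents do not support:
- **That the trial's inhibitor result is, or will be, reported backwards.** The documents contain no output and no production program. SAP 3.1 says the PTPs were already analysed in a report dated 14 March 2019 and are not analysed again here. The 83 PTPs in the protocol's revision history are not the 4.13.2 denominator either, since that depends on exposure days.
- **That the reversal is unconditional.** It needs `pos` to be a cell count and cases to be fewer than half.

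**Conclusion.** The point holds as a mismatch between the specified quantity and the example code for it. With `pos` as a cell count and cases in the minority, the code returns the inhibitor-free proportion and its limits. At the illustrative n of 13, the point estimate moves from 7.7% to 92.3% with one case and from 0% to 100% with none. The severity is low to moderate: the target in the prose is correct, the code is an example, and no information is lost because the limits mirror. It is not evidence that any reported result is wrong. The conclusion rests on standard PROC FREQ defaults, on the reading of `pos`, and, for the sizes only, on 13 evaluable PUPs.

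**What to change.** Amend the example block in SAP 4.13.2:
- delete `order=freq`;
- name the inhibitor-positive level, for example `tables inhibitor / binomial(level='<positive value>' exact);`, using the dataset's actual coding, which the SAP should state;
- use `weight pos / zeros;` and keep a positive row in the input even when its count is 0;
- define `pos` as the number of evaluable subjects at each level of `inhibitor`;
- add one sentence saying that the reported proportion is subjects with a confirmed inhibitor.

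While the block is open, state which interval applies with zero events. The code gives the two-sided limit (24.7% at n = 13), whereas the protocol calls for a one-sided interval (1 − 0.05^(1/13) = 20.6% if taken at 95%).

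The cost is a few words in one code block, with no effect on design, data or conduct. A quick check that the production programs name the positive level would settle the matter for the outputs.
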